4.1.2 Exclusion Criteria

- 1) <18 years old
- 2) Not Kaiser Permanente members
- 3) Not pregnant.
- 4) Not meeting the definition for the nine cohorts (pregnancy and depression/treatment status).

Subjects that do not meet all of the enrollment criteria may not be enrolled.

4.1.3 Populations

Stage I population

All KPNC women aged 18 years (legally allowed to participate in these types of studies at KPNC) or older who are pregnant and who participate in the universal peripartum depression screening will be eligible for the study. We expect that about 88,000 pregnant women will be

eligible during the study recruitment period. If a woman becomes pregnant a second time during the study period (an unlikely event given the short recruitment period of less than three years) and she was already in the study for her previous pregnancy, her second pregnancy will not be included in the study so as to avoid non-independent observations.

All participants in the universal depression screening will be identified and information on screening results, referrals, treatments, pregnancy related conditions and outcomes will be collected through linkage to various data sources of our comprehensive EMR system.

Stage II samples

A sample of 400 pregnant women from each of the nine cohorts previously described will be randomly selected to form Stage II samples. The random selection will be spread evenly throughout the study period so that all of the estimated 88,000 participants in Stage I will have an equal chance of being selected. They will be selected after their inclusion in Stage I with known status of depression and treatment, mostly before the 3rd trimester to avoid interviewing after delivery to reduce participation and recall biases. Any change in exposure status (depression and treatment) after initial assignment will be rectified and finalized during analyses, as we have done in other similar studies with two-stage design (with different exposures in pregnancy).

Participants in Stage II samples will be interviewed to obtain more detailed information on depression and its treatments. The Stage II samples will also allow for direct ascertainment of compliance with prescribed medications. Studies based on pharmacy data alone usually have to make an assumption of 100% compliance with dispensed medications. In this study, we can directly examine the compliance and assess its potential impact on treatment effectiveness. This will be an important strength for this study.

Through the interview, we will also directly ascertain compliance to prescribed medications for treating depression. We will make appropriate adjustment for compliance ratio in data analysis to more accurately estimate the treatment effectiveness after taking into account of non-compliance. In addition, we will also ascertain additional confounders including multivitamin intake during pregnancy and physical activity.

Informed consent will be obtained before the interview. All contact procedures will follow the standard contact and recruitment procedures as required by KPNC's IRB. Based on our experience with similar studies among KPNC pregnant women, a participation rate of 70-75% among eligible pregnant women can be expected. The recruitment will continue until 400 subjects from each of the nine cohort groups have completed the interview.

5 COMPARATORS

Comparators will vary depending on the research questions to be examined in analyses. The overall objective is to use appropriate comparators so that correct results of comparative effectiveness can be obtained after disentangling treatment effect from the effect of underlying depression (confounding by indication), and treatment benefits after balancing treatment benefit against the simultaneous risk of side effect (e.g., use of antidepressants). The following four cohorts (A-D) will be established within each depression type (depression only or depression with comorbidity) and various comparators will be used to answer the research questions in the Specific

Aims. We will also establish a control cohort (E) of women without depression for comparison of baseline risk.

Cohort A: women who screened positive and used antidepressants only. All women who screened positive for depression and were subsequently prescribed antidepressants during pregnancy will form Cohort A. Comparison of this cohort to Cohort D, a comparator for Specific Aim 1, will demonstrate the treatment effect of antidepressant use in reducing the fetal risk after controlling for severity of depressive symptoms and other confounders. Comparisons to Cohort B or C, comparators for Specific Aim 2, will determine which treatment option (antidepressant use, psychotherapy or combination therapy) is more effective in reducing fetal risk or has a better risk-benefit profile (pair-wise comparisons). Results from such comparisons will provide valuable information for clinicians as well as pregnant women to make an informed decision on the treatment options for depression during pregnancy based on research evidence.

Cohort B: women who screened positive and received psychotherapy only. This cohort consists of women who screened positive and subsequently received psychotherapy during pregnancy, but did not take any antidepressants. Comparison to Cohort D will determine if mitigation of depression by psychotherapy reduces fetal risk, after controlling for depression severity. Comparisons of this cohort to antidepressant use (Cohort A) or combination therapy (Cohort C), two separate comparators for Specific Aim 2, will provide head-to-head assessment of comparative effectiveness of treatment regimens.

Cohort C: women who screened positive and used both antidepressants and psychotherapy. This will be a cohort similar to Cohort A and B except that women in this cohort received combination therapies after screening positive. We classify them in a separate cohort to make Cohorts A and B encompass more clearly defined exposures of antidepressants and psychotherapy (pure exposure groups). In addition, this cohort may allow us to examine the potential benefit of combination therapy. Like Cohorts A and B described above, they will be compared to untreated comparator (Cohort D) for Specific Aim 1 and other treatment comparators (Cohort A and B) for Specific Aim 2.

Cohort D: women who screened positive for depression, and did not obtain treatment. Pregnant women whose PHQ-9 score is ≥ 10 at either of two screening visits (the first prenatal visit and glucola visit) or who were diagnosed as having depression by their medical providers, but did not receive any treatment for depression during pregnancy, will be classified into this cohort. Comparison of this cohort to Cohort E (control cohort), a comparator for Specific Aim 3, will allow us to assess whether untreated depression during pregnancy increases fetal risk (i.e., PTD or LBW) without the interference of treatment effect. We can also examine potential dose-response relationships based on the severity of depression (PHQ-9 scores) and duration of depression (persistence of the symptoms in both screening visits vs. at only one of the visits). Importantly, this cohort can be used as a comparator for Cohorts A, B, and C to examine the effect of depression treatment after controlling for underlying depression and severity (untreated comparators).

Cohort E (controls): women who screened negative for depression in both visits and did not receive treatments for depression. This cohort consists of the largest number of pregnant women, those who have neither depression and concurrent psychiatric comorbidity, nor treatment during pregnancy. This cohort will serve as the comparator for determining the effect of untreated depression on fetal risk (i.e., PTD, LBW). It will also serve as a reference check for other

comparisons. For example, does the benefit of a treatment totally eliminate the risk of PTD associated with depression during pregnancy?

The categorization into each cohort will be finalized at the end of pregnancy based on whether a woman met the criteria throughout the pregnancy. Comparisons of Cohort A, B, C, vs. D respectively, will answer the question of whether treating depression during pregnancy improves fetal outcomes, reducing PTD or LBW associated with untreated depression after controlling for underlying depression severity. Pairwise comparisons among Cohort A, B and C will answer the question of which treatment is most effective in improving fetal outcomes and has the best risk-benefit profile.

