psychiatry, psychology, or behavioral modification. Information on PHQ-9 scores, referrals, patient's uptake (or decline) of prescribed treatments are also captured by our EMRs. Any clinical diagnosis and treatment of depression for those not captured by the screening will also be identified through EMRs. During the glucola visit (22-24 weeks of gestation), all women will be screened for depression a second time using the same screening process as the first prenatal visit.

Women being treated for depression before the screening will be identified (<2%) and analyzed as a separate group.

Depression severity will also be used for stratification (to control for confounding by indication) when conducting head-to-head comparison of treatment effect among various treatment options.

Depression type (with or without other psychiatric comorbidity) will be determined by identifying concurrent psychiatric disorders from KPNC EMRs including organic psychotic conditions, other psychoses, neurotic and personality disorder and other mental disorders. The expected number of women who have depression only and depression with comorbidity during the study period is listed in Figure 2.

Antidepressant use during pregnancy. Antidepressant use, including types, timing, and duration of use, will be ascertained both through the depression screening and EMR (i.e., pharmacy database). The KPNC pharmacy database captures all inpatient and outpatient prescriptions and dispensations. Because of a large financial incentive to obtain medications at KPNC (in most cases, medications are covered with minimal co-payments), the KPNC pharmacy database has been shown to capture 93-98% of prescription medications of varying types. Compliance of taking antidepressants will also be ascertained during interview.

Psychotherapy. KPNC EMR records any psychotherapy patients receive for depression. The information includes the type of therapies (individual or group), sources of the treatment (psychologist, behavioral modification specialist, or psychologist/social worker) and number of sessions attended.

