4.1 Study Population

4.1.1 Inclusion Criteria

- 1) Females \geq age 18
- 2) Kaiser members
- 3) Pregnant beyond 20 weeks of gestation during the recruitment period
- 4) Meeting the definition of one of the following nine cohorts:

Cohort A (depression only): pregnant women who are depressed and use only antidepressants

Cohort A (depression with comorbidity): pregnant women who are depressed and use only antidepressants

Cohort B (depression only): pregnant women who are depressed and receive psychotherapy only

Cohort B (depression with comorbidity): pregnant women who are depressed and receive psychotherapy only

Cohort C (depression only): pregnant women who are depressed and receive antidepressants and psychotherapy

Cohort C (depression with comorbidity): pregnant women who are depressed and receive antidepressants and psychotherapy

Cohort D (depression only): pregnant women who are depressed and receive no treatment

Cohort D (depression with comorbidity): pregnant women who are depressed and receive no treatment

Cohort E: pregnant women who are not depressed (screen negative) and receive no treatment

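### Cohort A is defined both by antidepressant use and by prescription; under the prescription wording, women who never start the drug pull A towards untreated Cohort D

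*Combined protocol and SAP*

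**What the plan says.** Two definitions of Cohort A stand side by side.

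- **By use.** The inclusion criteria (section 4.1.1) describe "pregnant women who are depressed and use only antidepressants". The opening summary and the Specific Aims (section 2) say the same in substance. So does the paragraph heading in section 5: "Cohort A: women who screened positive and used antidepressants only".
- **By prescription.** The sentence under that heading, which says who makes up the cohort, reads "All women who screened positive for depression and were subsequently prescribed antidepressants during pregnancy will form Cohort A".

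The other depressed cohorts in section 5 rest on what the woman actually had. For B: "This cohort consists of women who screened positive and subsequently received psychotherapy during pregnancy, but did not take any antidepressants". C is described as having used and received both modalities. D covers depressed women who "did not receive any treatment for depression during pregnancy, will be classified into this cohort".

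On data, section 3.1.3 says that patients' "uptake (or decline) of prescribed treatments are also captured by our EMRs", that the pharmacy database records dispensations as well as prescriptions, and that the number of psychotherapy sessions attended is recorded. Section 4.1.3 adds, on the basis of the stage-two interviews, "We will make appropriate adjustment for compliance ratio in data analysis". Section 6 gives no method for that adjustment. Section 5 ends by saying that cohort membership is finalised at the end of pregnancy according to whether the criteria were met.

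**The concern.** A programmer could code Cohort A either way and be following the plan. If the prescription sentence is coded, the basis of classification differs between cohorts:

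- A woman prescribed an antidepressant who never starts it enters A. By D's definition she is untreated.
- If she also attends psychotherapy, she fits A's sentence and B's definition.
- A woman referred to psychotherapy who never attends goes to D, not B.

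Never-starters are therefore counted as treated on the drug side and as untreated on the psychotherapy side. The estimates for Aim 1 (A versus D) and Aim 2 (A versus B) both depend on this label. Section 6.1 uses the exposure of all 88,000 stage-one women in the main estimator, so a misclassification at stage one carries through. Section 1 treats possible fetal harm from antidepressants as a central uncertainty, so hiding a harm matters as much as hiding a benefit.

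**Working it through.** **1. The plan's own figures.** Section 6.2.2 gives minimum detectable PTD hazard ratios of 1.69-1.83 for 400 versus 400 women, and 1.32-1.38 for an effective 1,600 versus 1,600 (two-sided 0.05, power 0.80, PTD rate 8-11%). Take the stated rate as the reference-group risk p1, set p2 = 1 − (1 − p1)^HR and events = n(p1 + p2), and solve Schoenfeld's formula, events = 4(1.96 + 0.84)² / (ln HR)². This gives 1.82 (8%) and 1.69 (11%) at 400 per arm, and 1.38 and 1.32 at 1,600 per arm. The figures reproduce, and none is in error on this point. They supply realistic effect sizes: 1.38 for harm and 1/1.38 = 0.72 for benefit.

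**2. Inputs for the dilution.**
- Risk in D: 9.5%, the midpoint PTD rate in section 6.2.2. Applying it to D is an assumption.
- f, the share of Cohort A that never starts: not in the documents; taken as 10%, 20% and 30%.
- Non-starters carry D's risk, and no compliance correction is applied. Both are assumptions.

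**3. Formulas.** Risk in starters pT = 1 − (1 − 0.095)^HR. Risk in A as labelled pA = (1 − f)·pT + f·0.095. Apparent HR, A versus D = ln(1 − pA) / ln(1 − 0.095). Apparent HR, A versus B, when B has the same true HR and no never-starters = ln(1 − pA) / ln(1 − pT).

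**4. One case in full** (true HR 0.72, f = 30%). pT = 1 − 0.905^0.725 = 0.0698. pA = 0.7 × 0.0698 + 0.3 × 0.095 = 0.0774. A versus D = 0.0806 / 0.0998 = 0.81. A versus B = 0.0806 / 0.0724 = 1.11.

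**5. Results.**

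| f | A vs D, true 0.72 | A vs B, both 0.72 | A vs D, true 1.38 | A vs B, both 1.38 |
|---|---|---|---|---|
| 0 | 0.72 | 1.00 | 1.38 | 1.00 |
| 10% | 0.75 | 1.04 | 1.34 | 0.97 |
| 20% | 0.78 | 1.08 | 1.30 | 0.94 |
| 30% | 0.81 | 1.11 | 1.26 | 0.92 |

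At a true HR of 1.00 nothing moves. With a larger true benefit for both (1/1.83 = 0.55), A versus B reads 1.08, 1.16 and 1.25.

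**6. Effect on the tests** (true HR 0.72, 1,600 per arm). Power for A versus D, from z = ½·√events·|ln HR| − 1.96 with events = 1,600(pA + 0.095), falls from 74% to 65%, 54% and 43% at f = 10%, 20% and 30%. The chance of declaring A and B different when both work equally rises from 5.0% to 5.9%, 8.5% and 13.0%. At 400 per arm that chance is 5.2%, 5.9% and 7.0%.

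**The case against.** The strongest reply is that one loosely worded sentence is being made to carry too much. Most of the text, including the eligibility criteria, defines A by use. The prescription sentence cannot be the whole rule, because read literally it would also sweep in every Cohort C woman. The records needed to classify by use are listed in section 3.1.3. Section 4.1.3 says changes in exposure status will be rectified at analysis. Section 6.1 plans dose and duration of use as time-dependent covariates, and a compliance adjustment is promised.

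Much of this stands. It shows that prescription is one of two definitions, and that the authors may well have meant use. It does not settle the matter. The prescription sentence is the one that says who forms the cohort, and no text ties membership of A to a dispensing. Rectification and end-of-pregnancy finalisation apply the same criteria. The dose analyses do not redefine the cohorts. The compliance adjustment draws on 3,600 interviews, concerns medication only and has no stated method.

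A reader might go further and infer that the plan tilts Aim 2 against antidepressants. The documents do not support that. The shift disfavours A only if antidepressants lower PTD risk; if they raise it, the dilution flatters A. Nor is A necessarily the only diluted cohort. Never-starters enter only A, but B has no minimum number of sessions, and section 6.1 gives fewer than four visits as an example of possible lack of effect.

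**Conclusion.** The concern holds as an unreconciled definition of a main exposure, one version of which gives a worse answer. Followed literally, the prescription sentence biases A towards D. It understates benefit or harm in Aim 1 and distorts A versus B in Aim 2, with the direction set by the sign of the true effect.

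The size cannot be derived from the documents. The figures above are an illustration that rests on the assumed 10-30% never-start share, on non-starters having D's risk and on no compliance correction. A lower never-start share, or a working correction, would make the shift smaller. It would be wrong to conclude that the study will certainly be run on prescriptions, since the use-based wording is the more frequent. The point is worth acting on because the ambiguity affects two aims and is cheap to remove.

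**What to change.** In section 5, replace the prescription wording with one receipt-based exposure rule for Cohorts A to D, and align the summary, section 2 and section 4.1.1 with it:

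- antidepressant exposure (A and C): at least one dispensing during pregnancy in the pharmacy database;
- psychotherapy exposure (B and C): at least one attended session during pregnancy;
- women prescribed but never dispensed an antidepressant: classified by what they actually received, so B if they attended psychotherapy and D if they had no treatment.

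This concerns classification for analysis only. It leaves the planned compliance adjustment in place; whether that belongs in the main or a supporting analysis is a separate choice for the investigators.

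The cost is a rewording and a change to the cohort algorithm. Section 3.1.3 says the dispensing and attendance records are already held. The downside is somewhat smaller Cohorts A and C.

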Point and interval estimates of the relative hazard of PTD associated with each treatment modality (A, B, C), relative to no treatment (D) will be calculated via semiparametric maximum likelihood estimates of Cox proportional hazards regression parameters, with adjustment for potential confounders, as described above. In determining potential confounders in our regression models, we will first examine risk factors that may be plausibly linked to depression and PTD. Inclusion of potential confounding factors in our final regression models will be evaluated based on comparison of adjusted and unadjusted relative hazard ratios⁷⁹. Departures from model assumptions will be assessed via diagnostic plots of weighted residuals and tests for interaction between exposure and time (gestational age). The assessment of confounding variables for inclusion in regression models and testing of model assumptions will be performed in the stage-two sample using standard software for fitting Cox regression models. After determining the appropriate set of confounders and that there are no departures from model assumptions, the stage-one information on primary exposure and outcome will be incorporated using the semiparametric maximum likelihood estimator. This process applies to analyses of the remaining aims.

These comparisons will allow us to assess possible treatment effects on reducing PTD through both pharmacotherapy and psychotherapy. When compared to untreated (Cohort D), the comparison will be made after controlling for underlying severity of depression as measured by PHQ-9 scores or clinical diagnosis of severity before treatment. Table 2 shows that depression severity is relatively comparable among comparison groups, allowing control for confounding by indication (underlying depression severity, a unique strength of the proposed study due to the availability of PHQ-9 scores through the universal depression screening).

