We will also examine the possible dose-response in the association between antidepressant use and PTD by examining dosage of use, duration of the use, and timing of effect (single vs. multiple trimesters), in the context of time-dependent covariates. Similarly, we will also assess any dose-response relationship in the association between psychotherapy and PTD (the number of sessions received) and the effect of timing of treatment, also both as time-dependent covariates. If sample sizes allow, we will also examine the effect of combination of dose and timing (e.g., dose-response during early and late pregnancy). In addition, we will examine difference in the type of antidepressants (SSRI vs. non-SSRI).

Analyses of LBW as the outcome will parallel those described above for PTD, but logistic regression techniques will be used rather than Cox regression.

Aim 2. Head-to-head comparison of treatment regimens among Cohorts A, B & C, respectively

We will obtain point and interval estimates of relative hazards of PTD associated with the three pairwise contrasts among the three treatment groups. These estimates, and associated tests of significance, will be obtained using the Cox proportional hazards regression model developed in addressing Aim 1, fully adjusted for potential confounders including depression severity, as described above, via transformed linear contrasts of treatment group associated regression parameters. Based on the results of Aim 1 analyses of dose-response, we will obtain confounder adjusted relative hazards associated with PTD with levels of dose of a given treatment modality

(e.g. antidepressants, <30 days, 30-120 days, > 120 days duration during pregnancy), vs. particular levels of dose of another treatment (e.g. psychotherapy, ≥ 4 visits that has shown to be effective). We would categorize the comparator treatment (e.g., psychotherapy), based on the Aim 1 findings that the effectiveness of the comparator treatment in reducing risk of PTD varied by dose (e.g. no effect for < 4 visits).

As a secondary (exploratory) analysis, we will evaluate the treatment effectiveness separately for those with more severe underlying depression before treatment vs. those with more mild depression. Treating depression may be more beneficial for those with severe depression.

Analyses of LBW as the outcome will parallel those described above for PTD, but logistic regression techniques will be used rather than Cox regression.

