6.2.2 Sample size and statistical power

We expect to measure primary exposures (depression and treatment), and outcomes of interest (PTD, LBW) in approximately 88,000 women (stage-one sample). Randomly sampling from the stage-one cohort, we expect to recruit 400 pregnant women from each cohort (see Figure 2). Given the lack of methods for power calculations for the semiparametric maximum likelihood estimator (SMLE) in our two-stage sampling scheme, we very conservatively present minimum detectable effect calculations assuming the second stage sample of 3,600, noting that the gains in precision and statistical power in utilizing the measurements in stage-one sample of 88,000 women will be significant. In a small simulation study described below, we examine efficiency gains of an ad-hoc two-stage relative hazard estimator currently under investigation, which is an alternative to the semiparametric maximum likelihood estimator, attractive in its simplicity. These results provide information on the efficiency gains that can be expected in our two-stage design with the maximum likelihood estimation; the maximum likelihood estimator will be more efficient than the ad-hoc. Given results of the preliminary simulation study, we also present below estimates of minimum detectable effects using the two-stage SMLE for most estimates (in brackets, assumptions described below). Power calculations are based on the likelihood ratio test in the context of a Cox proportional hazards regression analysis and a logistic regression analyses, as appropriate to the outcome^{89 90}.

Given previous experience^{3,91-93}, we expect negligible loss to follow-up (< 1%). Based on our experience with our study population⁹⁴, we expect a rate of PTD (gestational age < 37 weeks) ranging from 8% - 11% and LBW ranging from 5% to 10%.

Each primary contrast of interest in analyses addressing **Aims 1 through 3** can be characterized as a comparison of two groups of 400 women with respect to risk of study outcomes of interest (N=800). Minimum detectable hazard ratios for PTD range from 1.69 – 1.83 across the range in expected rate of PTD (Table 5). Minimum detectable odds ratios for LBW range from 1.67 to 2.05 across the range in expected event rate.

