Relevant to **Aim 4** analyses of heterogeneity in the association between treatment/depression and PTD by psychiatric comorbidity status (yes/no with 50% of total stage 2 sample in each of the two groups), the minimum detectable hazard ratio for effect modification (interaction) was calculated, assuming a pairwise comparison of treatment effect (e.g. A vs. D) and the midpoint of the range in expected PTD rate (9.5%) [N for analyses = 1600]. The hazard ratio for effect modification is interpreted as the factor by which exposure to the effect modifier (comorbidity status = yes) increases the hazard ratio associated with treatment, over and above that in those unexposed to the effect modifier (comorbidity status = no). Using methods as outlined above, the minimum detectable hazard ratio for effect modification is 1.50, and similarly for analyses of LBW, the minimum detectable odds ratio for effect modification is 1.62 (two-sided test, $\alpha=.05$, power =.80). While this stratification analysis is an *a priori* aim of the study with relevant clinical implications, we will be conservative in interpretation of our findings due to increased number of comparisons from stratification by depression type, though the need to adjust for multiple comparisons remains controversial⁹⁵⁻⁹⁷.

Table 4. Comparison of Maternal Age and Race/Ethnicity for Newborns between KPNC and the General Population in the KPNC Service Regions

Characteristics	KPNC Births (%)	All births in the KPNC Service Regions (%)
Maternal age		
< 20	12	10
20-29	43	52
30+	45	38
Maternal race/ethnicity		
Asian	15	16
Black	10	10

Table 5. Minimum detectable hazard ratios (HR) for preterm delivery and minimum detectable odds ratios (OR) for low birthweight in a pair-wise comparison of depression exposure/treatment categories (N=800); two-sided test, significance level (α) = .05, power (1- β) =.80.

Preterm Delivery (HR)		Low Birthweight	
Rate = 8%	Rate = 11%	Rate = 5%	Rate = 10%

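### Cohorts A, B and C are settled from all treatment up to delivery, so women who add a second treatment count in C from 20 weeks; this can bias the Aim 2 contrasts in either direction

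*Combined protocol and SAP*

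**What the plan says.** Section 5 (Comparators) defines Cohort C as screen-positive women who used both treatments, with no rule on order or timing. The reason for a separate cohort is purity of A and B: "We classify them in a separate cohort to make Cohorts A and B encompass more clearly defined exposures". Cohort B is strict: "This cohort consists of women who screened positive and subsequently received psychotherapy during pregnancy, but did not take any antidepressants". The section closes by settling membership at the end of pregnancy, on criteria met throughout. Section 4.1.3 (Stage II samples) adds that changes in treatment status after the initial assignment are put right during analysis.

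Section 6.1 starts follow-up at 20 weeks. The Aim 1 Cox model adjusts for "underlying severity of depression as measured by PHQ-9 scores or clinical diagnosis of severity before treatment". Aim 2 takes its pairwise comparisons from that same model as "transformed linear contrasts of treatment group associated regression parameters". The propensity model in section 6.1.1 uses the same covariates. Time-dependent covariates are specified for dose, duration and timing, but not for membership of A, B or C. LBW is analysed by logistic regression.

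**The concern.** Membership depends on treatment received during follow-up. A woman who starts psychotherapy and adds an antidepressant at, say, 28 weeks no longer meets the definition of B. The definition she does meet is C, and she is counted there from 20 weeks, including the weeks before the second treatment began.

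Two distortions follow in C versus A and C versus B.

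- **Selection on response.** If the second treatment is added because the first is not working, A and B lose their non-responders and C gains them. If non-responders have a higher PTD risk, this works against C.
- **Immortal time.** A woman must still be pregnant to add a treatment. One who delivers early has less opportunity and stays in A or B, while the event-free weeks before step-up are credited to C. This works in favour of C.

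Aim 2 is the head-to-head question of which treatment is more effective. A difference could be reported where none exists, or a real one hidden. The result would also be hard to use for a choice of first treatment, because the groups are defined partly by what happened after that choice.

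**Working it through.** **1. The plan's own yardstick.** Inputs from section 6.2.2: "two-sided test, significance level (α) = .05", "power (1- β) =.80", a "comparison of two groups of 400 women", and a PTD rate of 8% to 11%. Take that rate p as the reference-group rate.

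- Events needed (Schoenfeld, 1:1) = 4 × (1.960 + 0.842)² / (ln HR)².
- Events available = (N/2) × [p + 1 − (1 − p)^HR].
- Example: HR 1.83, N = 800, p = 8% needs 86 events and has 88.6.
- Solving for HR gives 1.82 and 1.69 at N = 800 (plan: 1.83 and 1.69), and 1.38 and 1.32 at the effective N = 3,200 (plan: 1.38 and 1.32).

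The plan's detectable hazard ratios are reproduced, so 1.32 to 1.38 is a fair yardstick for the size of a bias.

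**2. Selection alone, treatments equal.** All inputs here are assumed. Of women starting treatment, 30% are non-responders with PTD risk 12%; the others have 8%. Overall risk = 0.7 × 8 + 0.3 × 12 = 9.2%, inside the plan's range. A share s of non-responders steps up, no responder does, and step-ups form a share c of C.

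- Single-therapy risk = [0.7 × 8 + 0.3(1 − s) × 12] / [0.7 + 0.3(1 − s)]: 8.82% at s = 0.4, 8.32% at s = 0.8.
- Risk in C = (1 − c) × 9.2 + c × 12: 10.04% at c = 0.3, 10.6% at c = 0.5.
- Risk ratio: 10.04/8.82 = 1.14 to 10.6/8.32 = 1.27.

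This shows the selection bias only and leans on no responder stepping up. If 10% of responders also step up, the single-therapy risks become 8.89% and 8.35%, the step-ups' risks 10.53% and 11.10%, and the ratio 1.08 to 1.22. At 25% it is 1.03 to 1.16.

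**3. Both biases together, true HR 1.00.** This is a Cox simulation from 20 weeks in which a woman can step up only while still pregnant. Assumed: 40% non-response; 50% of non-responders and 0 to 25% of responders step up; 10% to 30% start on both; non-responders have 1 to 3 times the PTD risk.

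| Step-up weeks | HR, C vs single, non-responders at 1.5 to 3 times the risk |
|---|---|
| 12–24 | 1.06–1.80 |
| 12–36 | 0.96–1.59 |
| 20–36 | 0.91–1.52 |
| 24–36 | 0.87–1.43 |

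With no extra risk in non-responders, timing alone gives 0.80 to 1.00. Individual results for step-up at weeks 24–36, with 10% starting on both:

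| Risk of non-responders | Responders stepping up | HR, end-of-pregnancy class | HR, starting regimen |
|---|---|---|---|
| 1.0× | 25% | 0.80 | 1.01 |
| 1.5× | 0% | 1.02 | 0.99 |
| 2.0× | 25% | 0.90 | 1.00 |
| 2.0× | 0% | 1.19 | 1.01 |
| 3.0× | 0% | 1.43 | 1.01 |

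Across all scenarios, classification by starting regimen gives 0.98 to 1.02.

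**4. Chance of declaring a spurious difference.** At the plan's midpoint rate of 9.5%, events are 800 × 0.095 = 76 or 3,200 × 0.095 = 304. Probability = Φ(√(events/4) × |ln HR| − 1.96).

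| Spurious HR | 76 events | 304 events |
|---|---|---|
| 0.85 | 11% | 29% |
| 1.20 | 12% | 36% |
| 1.45 | 37% | 90% |

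**The case against.** **The reclassification is inferred.** No sentence says that a woman who steps up moves to C. It follows from sections 4.1.3 and 5 read together. The phrase about meeting the criteria throughout pregnancy, with exclusion criterion 4 in section 4.1.2, could also be read as dropping women who change regimen. C would then not be enriched, but A and B would still lose these women on the basis of later treatment. The ambiguity stands and needs settling in either case.

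**A reader might infer that combination therapy must look worse.** The documents do not support that. Early delivery limits the chance to step up, and this pull towards C can offset or reverse the selection effect.

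**A reader might also infer that A and B are flattered against D in Aim 1.** That is not shown. D requires no treatment at any time in pregnancy, so untreated women who worsen and then accept treatment leave D as well.

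**The plan has relevant tools.** These are a second PHQ-9 at 22–24 weeks (section 3.1.3), time-dependent dose and timing analyses (6.1), and an instrumental-variable analysis (6.1.2). None is assigned to this problem. The instrumental-variable analysis is a sensitivity check and sets no rule for sequential treatment.

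**Groups of pure exposure are a legitimate target.** So they are, but comparing treatment actually received calls for time-varying treatment and time-varying severity, not a fixed label assigned after follow-up.

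**The size is assumed.** This is correct. In step 2 even the top value of 1.27 is below the plan's smallest detectable hazard ratio. With step-up at weeks 24–36, passing 1.38 took threefold risk in non-responders and no responder stepping up.

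**Conclusion.** The concern holds in this form: C versus A and C versus B can show a difference when the treatments are equal, and adjustment for pre-treatment severity, by regression or propensity score, cannot remove it. Two biases of opposite sign act together, and the documents do not allow the net direction to be worked out. The simulated null hazard ratios of 0.80 to 1.80 are illustrations resting on assumed rates of non-response and step-up, step-up timing, and excess risk. They show that the bias can matter against a detectable 1.32 to 1.38, not that it will. They also depend on when preterm deliveries occur: the more of them that fall early, the stronger the pull in favour of C. The 1.14 to 1.27 illustrates the selection bias alone. The point deserves a change before analysis, because it touches a main aim and the remedy is inexpensive.

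**What to change.** For the primary Aim 2 contrasts, and for the Aim 1 model from which they are drawn:

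1. Classify each treated woman by the regimen started within a short fixed window after her qualifying screen (30 days, for example). She is in C only if both treatments start in the window; otherwise she is in A or B by the first started.
2. Keep that class after later additions. State also where a woman belongs whose first treatment starts after the window.
3. Start follow-up for all compared groups at the later of the window's end or 20 weeks.
4. Use the same classification for LBW.
5. Report the current end-of-pregnancy grouping as a sensitivity analysis, with simultaneous starters and step-ups shown separately.

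If treatment received is to stay the target, the alternative is time-dependent treatment with time-varying severity, including the 22–24 week PHQ-9, in a marginal structural model.

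**Cost.** Protocol and SAP wording, plus start dates for both treatments. The pharmacy database holds timing of antidepressant use, and the planned time-dependent analysis of psychotherapy sessions needs dates in any case. C becomes smaller, so its contrasts lose precision. A and B become starting strategies that include some later add-on treatment, so the purity sought in section 5 is given up in the primary analysis. Confounding in the choice of first regimen remains, and still relies on the planned severity adjustment.
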